## 1 Protocol Summary

### 1.1 Synopsis

**Name of Sponsor:**

Otsuka Pharmaceutical Development & Commercialization, Inc. (OPDC)

**Name of Investigational Medicinal Product:**

Vadadustat

**Protocol No.:**

404-201-00012

**IND No.:**

102,465

**EudraCT No.:**

2019-004851-36

**Protocol Title:**

Phase 3b, Randomized, Open-label, Active-controlled Trial Evaluating the Efficacy and Safety of Oral Vadadustat Once Daily (QD) and Three Times Weekly (TIW) for the Maintenance Treatment of Anemia in Hemodialysis Subjects Converting from Erythropoiesis-stimulating Agents (ESAs)

**Clinical Phase:**

3b

**Treatment/Indication:**

Anemia of chronic kidney disease (CKD)

**Objectives and Endpoints:**

The primary objective of the trial is to demonstrate the efficacy and safety of vadadustat compared to darbepoetin alfa for the maintenance treatment of anemia in hemodialysis subjects after conversion from current ESA therapy.

Primary efficacy endpoints of the trial include efficacy parameters for change in hemoglobin (Hb) between Baseline (average pretreatment Hb) and the primary evaluation period (average Hb from Weeks 20 to 26, inclusive).

Key secondary efficacy endpoints of the trial include efficacy parameters for change in Hb value between Baseline (average pretreatment Hb) and the secondary evaluation period (average Hb from Weeks 46 to 52).

Other efficacy endpoints of the trial include the following:

- Proportion of subjects having average Hb values within the target range during the primary evaluation period (Weeks 20 to 26).
- Proportion of subjects having average Hb values within the target range during the secondary evaluation period (Weeks 46 to 52).
- Proportion of subjects receiving intravenous (IV) iron therapy from Baseline to Week 52.
- Average monthly dose of IV elemental iron administered from Baseline to Week 52 in subjects who have received IV elemental iron.
- Receipt of ESA rescue.
- Proportion of subjects receiving red blood cell (RBC) transfusions from Baseline to Week 26.
- Proportion of subjects receiving RBC transfusions from Baseline to Week 52.
- Change from Screening Visit 2 36-Item Short Form (SF-36v2) Health-related Quality of Life (HRQOL) scores.
- Change from Screening Visit 2 to the average value in Anemia Subscale ("Additional Concerns") of Functional Assessment of Cancer Therapy-Anemia (FACT-An) Score.
- Change from Screening Visit 2 to the average value in Total FACT-An Score.
- Change from Screening Visit 2 in score of Patient Global Impression of Severity (PGI-S).
- Score of Patient Global Impression of Change (PGI-C).

Safety endpoints of the trial include adverse events (AEs) and serious adverse events (SAEs), vital sign measurements, electrocardiograms (ECGs) and clinical laboratory values, episodes of Hb  $> 12.0$  g/dL,  $> 13.0$  g/dL, or  $> 14.0$  g/dL, and the number of episodes of Hb increase  $> 1.0$  g/dL within any 2-week interval or  $> 2.0$  g/dL within any 4-week interval.

Pharmacokinetic (PK): no PK analysis will be conducted. Vadadustat plasma concentrations may be included in a population PK analysis reported separately.

Pharmacodynamic (PD) endpoints of the trial include parameters erythropoietin (EPO), reticulocytes, and markers of iron metabolism (iron, ferritin, total iron binding capacity [TIBC], etc.).

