## 2.4 Known and Potential Risks and Benefits

Please see the vadadustat IB for additional information.

Trials of injectable ESAs in patients with anemia secondary to NDD-CKD or DD-CKD have demonstrated an increased risk of CV events associated with higher Hb targets. Post-hoc analyses performed by the Food and Drug Administration (FDA) and others have shown an association between these adverse outcomes and supraphysiologic serum EPO levels and/or Hb oscillations and overshoots. In studies to date, oral vadadustat daily increased mean Hb with few excursions above the target range. In addition, serum EPO levels remained well below those reported with ESAs in the literature. As a result, there is the potential for the investigational drug vadadustat to provide an effective and safe therapeutic option for the treatment of renal anemia.

In addition, vadadustat may enhance iron metabolism and transport. phase 1 and phase 2 studies have demonstrated a consistent dose-dependent increase in TIBC and decrease in ferritin and hepcidin. Mechanistic studies have demonstrated that HIF stabilization downregulates the iron absorption regulator hepcidin, and upregulates the iron-mobilizing regulators ferroportin and transferrin (and its receptor). Potential clinical benefits include enhanced erythropoiesis and decreased exogenous iron requirements.

In nonclinical safety studies, the main findings originated from an exaggerated pharmacological response that results in increased erythropoiesis, polycythemia, blood hyperviscosity, and the formation of fibrin thrombi in multiple organs. Early mortality noted in the mouse and rat and moribundity in the dog were due to the sequelae associated with polycythemia. These findings were reproducible across species and

studies, dose-dependent and showed reversibility. Dose-limiting toxicity in the exploratory toxicology studies was due to hemoglobinuric nephropathy (rat) and emesis associated with body weight loss (dog).

In completed phase 1 clinical studies of vadadustat in healthy subjects, there were low numbers of treatment-emergent AEs. The most frequently reported AEs were in the gastrointestinal disorders (ie, nausea, diarrhea, abdominal pain, flatulence, dyspepsia) and nervous system disorders (ie, headache, dizziness) SOC. The majority of AEs were mild to moderate in severity.

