## **6.5 Concomitant Medications or Therapies**

The investigator will record all medications and therapies taken by the subject from 8 weeks prior to signing of informed consent through the Safety Follow-up Visit on the eCRF. The investigator will also record all medications and therapies taken by the subject for treatment of an AE or which caused an AE until the end of the trial (defined as the last date of contact or date of final contact attempt) on the eCRF.

Erythropoiesis-stimulating agents (ESAs), blood transfusions, and iron treatment regimen prior to randomization and the date of last dose will be recorded on a separate disease-related concomitant therapy eCRF pages.

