The proportion of subjects receiving at least one intravenous (IV) iron therapy from Baseline to Week 52 will be calculated, and a Mantel-Haenszel estimation of risk difference stratified by the baseline strata will be performed.

In addition, the following subgroups of baseline iron will be performed:

- Subjects not receiving any iron at baseline, and
- Subjects receiving IV or oral iron at baseline.

9.4.4 Average Weekly Dose of IV Elemental Iron Administered from Baseline to Week 52

Average weekly dose of IV elemental iron administered from Baseline to Week 52 in subjects who have received IV elemental iron will be calculated, and an analysis of variance (ANOVA) model with 2 stratification factors at randomization will be performed. If the distribution is highly skewed because of a long tail to the right, other methods may be considered.

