14.2.3.2.1	Proportion of Subjects Having Average Hb Values within the Target Range during Secondary Efficacy Period (Weeks 46 to 52)	Randomized Population
14.2.3.2.2	Proportion of Subjects Having Average Hb Values within the Target Range during Secondary Efficacy Period (Weeks 46 to 52)	Full Analysis Set Population
14.2.4.1.1	Proportion of Subjects Receiving IV Iron Therapy by Baseline Iron Group	Randomized Population
14.2.4.1.2	Proportion of Subjects Receiving IV Iron Therapy by Baseline Iron Group	Full Analysis Set Population
14.2.4.2.1	Average Weekly Dose (mg) of IV Elemental Iron Administered in Subjects Who Have Received IV Elemental Iron	Randomized Population
14.2.4.2.2	Average Weekly Dose (mg) of IV Elemental Iron Administered in Subjects Who Have Received IV Elemental Iron	Full Analysis Set Population

Table Number	Table Title	Population
14.2.4.3.1.1	Proportion of Subjects with any ESA Rescue Medications - Narrow Therapy with $\geq 50\%$ Increases in Darbepoetin Alfa Treatment	Randomized Population
14.2.4.3.1.2	Proportion of Subjects with any ESA Rescue Medications - Narrow Therapy with $\geq 50\%$ Increases in Darbepoetin Alfa Treatment	Full Analysis Set Population
14.2.4.3.2.1	Proportion of Subjects with any ESA Rescue Medications - Narrow Therapy with $\geq 100\%$ Increases in Darbepoetin Alfa Treatment	Randomized Population
14.2.4.3.2.2	Proportion of Subjects with any ESA Rescue Medications - Narrow Therapy with $\geq 100\%$ Increases in Darbepoetin Alfa Treatment	Full Analysis Set Population
14.2.4.3.3.1	Proportion of Subjects with any ESA Rescue Medications - Broad-on-treatment Therapy with $\geq 50\%$ Increases in Darbepoetin Alfa Treatment	Randomized Population
14.2.4.3.3.2	Proportion of Subjects with any ESA Rescue Medications - Broad-on-treatment Therapy $\geq 50\%$ Increases in Darbepoetin Alfa Treatment	Full Analysis Set Population
14.2.4.3.4.1	Proportion of Subjects with any ESA Rescue Medications - Broad-on-treatment Therapy with $\geq 100\%$ Increases in Darbepoetin Alfa Treatment	Randomized Population
14.2.4.3.4.2	Proportion of Subjects with any ESA Rescue Medications - Broad-on-treatment Therapy with $\geq 100\%$ Increases in Darbepoetin Alfa Treatment	Full Analysis Set Population
14.2.4.4.1	Time to First ESA Rescue Medication - Narrow Therapy with $\geq 50\%$ Increases in Darbepoetin Alfa Treatment	Randomized Population

Table Number	Table Title	Population

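### Neither overall IV iron comparison (SAP 9.4.3 and 9.4.4) adjusts for the recorded pre-randomization iron regimen, baseline ferritin or baseline TSAT

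*Protocol*

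**What the plan says.** **Endpoints.** The Protocol Synopsis and Table 3-1 list two IV iron endpoints among the other efficacy endpoints: the proportion of subjects receiving IV iron to Week 52, and "Average monthly dose of IV elemental iron administered from Baseline to Week 52 in subjects who have received IV elemental iron". The SAP expresses the dose per week. Its revision table records that change, so the difference is not an error.

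**Dose (SAP 9.4.4).** The stated model is that "an analysis of variance (ANOVA) model with 2 stratification factors at randomization will be performed". SAP 2.1 gives the two factors as region and prior ESA dose group. The section allows other methods if the distribution has a long right tail.

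**Proportion (SAP 9.4.3).** For the overall comparison, "a Mantel-Haenszel estimation of risk difference stratified by the baseline strata will be performed". I read the baseline strata as the four region by ESA-dose cells. Two subgroups are added: subjects on no iron at baseline, and "Subjects receiving IV or oral iron at baseline". In SAP Section 19, Tables 14.2.4.1.1 and 14.2.4.1.2 are titled "Proportion of Subjects Receiving IV Iron Therapy by Baseline Iron Group". For dose, only Listing 16.2.6.2 is by baseline iron group; the dose tables are not.

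**What is collected.** Protocol 6.5 says that the "iron treatment regimen prior to randomization and the date of last dose will be recorded" on dedicated eCRF pages, and it records all medications from 8 weeks before consent. Ferritin and TSAT are eligibility tests (Protocol 5.2.1), and the Schedule of Assessments has iron indices at Screening and at Baseline. SAP 5.2 already defines baseline for such parameters as the last value before first dose.

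**The concern.** Protocol 2.4 gives lower iron need as a reason to expect benefit: "Potential clinical benefits include enhanced erythropoiesis and decreased exogenous iron requirements". The two IV iron endpoints are where the trial looks for it.

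Protocol 6.5.2.1 ties iron supplementation to ferritin and TSAT levels. Iron stores at entry, and iron use before entry, are therefore plausible predictors of IV iron during the trial. Leaving a predictor out of the model keeps its variance in the error term and widens the interval. It also leaves the point estimate exposed to chance differences between arms in prior iron use.

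SAP Section 9 makes ANCOVA or MMRM the general approach for continuous outcomes, and the primary analysis adjusts for baseline Hb. IV iron dose has a natural pre-randomization counterpart, yet its model contains none.

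**Working it through.** **1. The plan's own figure.** The only power statement concerns the primary Hb test: above 90% with 100 per arm and 30% dropout (Protocol 9.1). With 100 × 0.70 = 70 evaluable per arm, SD 1.2 and margin 0.75, power = Φ(0.75 / (1.2 × √(2/70)) − 1.96) = Φ(3.70 − 1.96) = 95.9%. The statement is reproduced. It has no bearing on IV iron, for which the documents give no SD, event rate or power.

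**2. Dose endpoint.** Let R be the partial correlation of the baseline iron variables with on-trial IV iron dose, given the two stratification factors, among recipients. Then SE with covariates / SE without = √(1 − R²), and the equivalent sample-size factor is 1/(1 − R²). The documents do not give R, so the range below is assumed.

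| R (assumed) | SE ratio | CI narrower by | Equivalent sample size |
|---|---|---|---|
| 0.2 | 0.980 | 2.0% | 1.04× |
| 0.3 | 0.954 | 4.6% | 1.10× |
| 0.5 | 0.866 | 13.4% | 1.33× |
| 0.7 | 0.714 | 28.6% | 1.96× |

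Assume also 60 recipients per arm. The difference detectable with 80% power is (1.96 + 0.84) × √(2/60) × √(1 − R²): 0.51 SD at R = 0, then 0.49, 0.44 and 0.37 SD at R = 0.3, 0.5 and 0.7.

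**3. Proportion endpoint.** Take 100 per arm with the same rates in both arms and, for simplicity, ignore the existing strata. Let q be the share on iron at baseline, and p1 and p0 the on-trial IV iron rates with and without it. Total variance is p(1 − p) with p = q·p1 + (1 − q)·p0. Within-stratum variance is q·p1(1 − p1) + (1 − q)·p0(1 − p0). The 95% half-width is 1.96 × √(2 × variance / 100). All rates are assumed.

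| q | p1 vs p0 | Total variance | Within-stratum variance | Half-width before → after (points) |
|---|---|---|---|---|
| 0.6 | 70% vs 50% | 0.236 | 0.226 | 13.5 → 13.2 |
| 0.5 | 80% vs 40% | 0.240 | 0.200 | 13.6 → 12.4 |
| 0.6 | 85% vs 25% | 0.238 | 0.152 | 13.5 → 10.8 |

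**4. Chance imbalance.** If half the subjects used IV iron before the trial (assumption), the SD of the difference between two arms is √(2 × 0.5 × 0.5 / 100) = 7.1 points. A gap of 10 points or more has probability 2 × (1 − Φ(1.41)), about 16% per comparison.

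**5. What adjustment does not repair.** The dose analysis keeps only subjects who received IV iron after randomization. In an illustrative simulation, a measured baseline variable and an unmeasured one both affected receipt and dose. Receipt was 60% in one arm and 40% in the other, with no treatment effect on dose itself (mean 100, SD 40, arbitrary units). The recipients-only difference was +8.2 units unadjusted and still +5.7 after adjusting for the measured variable, against a true value of 0. The inputs are assumed; the example shows the mechanism, not its size in this trial.

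**6. Strata.** Region × ESA dose gives 2 × 2 = 4 cells, and a yes/no iron factor makes 8. About 90 European subjects over three arms is about 60 per pairwise comparison, or 15 per cell on average over four European cells.

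**The case against.** **The plan does look at baseline iron.** A reader might infer that prior iron use is ignored altogether. The documents do not support that: SAP 9.4.3 prespecifies the two baseline iron subgroups, with tables and a dose listing by the same grouping. What stands is narrower. The subgroups apply only to the proportion, pool IV with oral iron although the outcome is IV iron, omit ferritin and TSAT, and split the sample instead of adjusting the overall estimate.

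**The planned proportion analysis is valid.** A reader might infer that it is biased. It is not: it compares randomized arms, and its interval already allows for chance imbalance. The issue is precision.

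**Noise is not the main weakness of the dose endpoint.** This objection is right. Restricting to recipients is a selection made after randomization, and a narrower interval around that contrast could invite more confidence than it deserves. Adjustment should not be presented as a cure.

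**The covariates may be weak.** Entry requires ferritin of at least 100 ng/mL and TSAT of at least 20%, which truncates the low end. Subjects who fail on iron may be rescreened after replacement (Protocol 5.4.1), so a recent dose can reflect one-off repletion. Both points argue for the lower part of the range of R.

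**It is not entirely free.** The regimen is recorded, but I found no defined pre-randomization average weekly IV iron dose. One must be derived, and the strata become smaller.

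**Conclusion.** The point holds as a low-priority improvement in precision. The dose model contains no baseline iron variable, and the overall proportion comparison uses none as a stratification factor, although the information is collected before treatment.

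The gain cannot be fixed from the documents. On assumed inputs the dose interval narrows by about 5% to 13% for R between 0.3 and 0.5, and the half-width for the proportion falls by anything from 0.3 to 2.7 points.

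Two limits apply. Adjustment does not turn the recipients-only dose analysis into a randomized comparison. And SAP 9.4 and 9.5 place both endpoints among the other endpoints, without multiplicity correction and outside the testing hierarchy, so no confirmatory conclusion depends on this.

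**What to change.** **SAP 9.4.4.** Replace the ANOVA with an ANCOVA containing treatment, the two stratification factors, pre-randomization average weekly IV elemental iron dose (0 if none), baseline ferritin and baseline TSAT. State the lookback; the period from 8 weeks before consent, already recorded under Protocol 6.5, would serve. Carry the same covariates into any alternative method used for skewed data. State in the section that the analysis is restricted to recipients and is not a randomized comparison.

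**SAP 9.4.3.** Add IV iron use at baseline (yes/no, same lookback) as a Mantel-Haenszel stratification factor in the overall comparison. Keep the two planned subgroups.

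**Cost.** SAP wording and one derived variable, with no new visits or measurements. The Mantel-Haenszel strata rise from four to eight, and the European cells will be small.

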### **Trial Design:**

Phase 3b, randomized, open-label, active-controlled trial of vadadustat versus darbepoetin alfa for the maintenance treatment of anemia in hemodialysis subjects, after conversion from ESA therapy.

Following a Screening period of up to 8 weeks (56 days), subjects who meet all eligibility criteria will be randomized 1:1:1 to vadadustat QD, vadadustat TIW, or darbepoetin alfa. Target enrollment in this trial is an estimated 300 subjects at up to 150 investigative sites in the United States (US) and Europe.

Subjects will be randomized at the Baseline Visit using an Interactive Web Response (IWR) system to receive either vadadustat QD, vadadustat TIW, or darbepoetin alfa.

Randomization will be stratified with respect to:

- Geographic region (US versus Europe, approximately 90 subjects in Europe).
- Mean weekly darbepoetin alfa dose (or ESA equivalent) calculated over a period of 8 weeks prior to Screening Visit 2:
  - Low darbepoetin alfa dose group ( $\leq 0.45 \mu\text{g/kg/week}$ ).
  - High darbepoetin alfa dose group ( $> 0.45$  and  $\leq 1.5 \mu\text{g/kg/week}$ ).

In each stratum, there will be 3 arms: vadadustat QD, vadadustat TIW, and darbepoetin alfa.

Following screening and randomization, there will be 2 periods during the trial:

- **Conversion and Maintenance Treatment Period (Weeks 0 to 52):** conversion to investigational medicinal product (IMP) for maintaining Hb (Weeks 0 to 20), primary efficacy evaluation (Weeks 20 to 26), and secondary efficacy evaluation (Weeks 46 to 52).
- **Safety Follow-up Period (Early Termination [ET] and Follow-up):** post-treatment Safety Follow-up Visit (ET/End of Treatment [EOT] + 4 weeks) (in person).

Individual subjects will participate in total trial duration of approximately 64 weeks.

A structured exit interview may be conducted at the EOT Visit at a subset of sites.

### **Trial Population:**

An estimated 300 subjects with approximately:

- 100 subjects randomized to vadadustat QD arm.
- 100 subjects randomized to vadadustat TIW arm.
- 100 subjects randomized to darbepoetin alfa arm.

The trial population will consist of subjects  $\geq 18$  years of age receiving chronic, outpatient in-center hemodialysis TIW, with 2 screening Hb values between 8.0 and 11.0 g/dL (inclusive) in the US or between 9.0 and 12.0 g/dL (inclusive) in Europe, and on maintenance treatment with an ESA.

**Inclusion Criteria:**

Subjects are required to meet the following inclusion criteria:

- 1)  $\geq 18$  years of age.
- 2) Receiving chronic, outpatient TIW hemodialysis for end-stage renal disease for at least 12 weeks prior to Screening.
- 3) Hemodialysis adequacy as indicated by single-pool  $K_t/V_{urea} \geq 1.2$  using the most recent historical measurement within 8 weeks prior to or during Screening.
- 4) Use of any approved ESA for at least the 8 weeks prior to Screening Visit 2.
- 5) Two Hb values, at least 4 days apart, measured by the central laboratory during Screening within the following prespecified ranges:
  - a) Hb values between 8.0 and 11.0 g/dL (inclusive) in the US.
  - b) Hb values between 9.0 and 12.0 g/dL (inclusive) in Europe.
- 6) Serum ferritin  $\geq 100$  ng/mL and transferrin saturation (TSAT)  $\geq 20\%$  during Screening.
- 7) Folate and vitamin B12 measurements  $\geq$  lower limit of normal during Screening.

**Exclusion Criteria:**

Subjects will be excluded if they meet any of the following exclusion criteria:

- 1) Women of childbearing potential (WOCBP) who do not agree to practice 2 different methods of birth control or remain abstinent during the trial and for 30 days after the last dose of IMP. If employing birth control, 2 of the following precautions must be used: vasectomy of partner, tubal ligation, vaginal diaphragm, or intrauterine device.
- 2) Male subjects who have not had a vasectomy and do not agree to the following: use of an acceptable form of contraception during the study and for 30 days after the last dose of the study drug; to not donate semen during the study and for at least 30 days after the last dose of vadadustat.
- 3) Women who are breast feeding and/or who have a positive pregnancy test result prior to receiving IMP.
- 4) Subjects with contraindication to required trial assessment.
- 5) Subjects who, in opinion of the investigator or medical monitor, have a medical history or medical findings inconsistent with safety or trial compliance.

- 6) Anemia due to a cause other than CKD (eg, sickle cell disease, myelodysplastic syndromes, bone marrow fibrosis, hematologic malignancy, myeloma, hemolytic anemia, thalassemia, or pure red cell aplasia).
- 7) Subjects meeting cut-off of the following equivalent mean weekly doses calculated over 8 weeks prior to Screening Visit 2:
  - a) Methoxy polyethylene glycol-epoetin beta > 50 µg/week.
  - b) Darbepoetin alfa > 100 µg/week.
  - c) Epoetin analogues > 23000 IU/week.
- 8) Active bleeding or recent blood loss within 8 weeks prior to randomization.
- 9) Red blood cell transfusion within 8 weeks prior to randomization.
- 10) Anticipated to discontinue hemodialysis during the trial.
- 11) Judged by the investigator that the subject is likely to need rescue therapy (ESA administration or RBC transfusion) immediately after enrollment in the trial.
- 12) History of chronic liver disease (eg, chronic infectious hepatitis, chronic autoimmune liver disease, cirrhosis, or fibrosis of the liver).
- 13) Aspartate aminotransferase (AST)/serum glutamic oxaloacetic transaminase (SGOT), alanine aminotransferase (ALT)/serum glutamic pyruvic transaminase (SGPT), or total bilirubin > 1.5 x upper limit of normal (ULN) during Screening. Subjects with a history of Gilbert's syndrome are not excluded.
- 14) Current uncontrolled hypertension as determined by the investigator that would contraindicate the use of an ESA.
- 15) Acute coronary syndrome (hospitalization for unstable angina or myocardial infarction), surgical or percutaneous intervention for coronary, cerebrovascular or peripheral artery disease (aortic or lower extremity), surgical or percutaneous valvular replacement or repair, sustained ventricular tachycardia, hospitalization for heart failure (HF) or New York Heart Association Class IV HF, or stroke within 12 weeks prior to or during Screening.
- 16) History of new or recurrent malignancy within 2 years prior to and during Screening or currently receiving treatment or suppressive therapy for cancer. Subjects with treated basal cell carcinoma of skin, curatively resected squamous cell carcinoma of skin, or cervical carcinoma in situ are not excluded.
- 17) History of a new or recurrent episode of deep vein thrombosis or pulmonary embolism within 12 weeks prior to or during Screening.
- 18) History of hemosiderosis or hemochromatosis.
- 19) History of prior organ transplantation (subjects with a history of failed kidney transplant or corneal transplants are not excluded).
- 20) Scheduled organ transplant from a living donor and subjects on the kidney transplant wait-list who are expected to receive a transplant within 6 months.
- 21) History of a prior hematopoietic stem cell or bone marrow transplant (stem cell therapy for knee arthritis is not excluded).
- 22) Known hypersensitivity to vadadustat, darbepoetin alfa, or any of their excipients.

- 23) Use of an investigational medication within 30 days or 5 half-lives of the investigational medication (whichever is longer), prior to screening or during screening and any prior use of a hypoxia-inducible factor prolyl hydroxylase inhibitor. Subjects may participate in another concurrent trial only if that trial is a non-interventional, observational investigation.
- 24) Subjects with bilateral native nephrectomy.
- 25) Treated with probenecid within the 28-day Screening Period prior to randomization or during the study treatment duration.
- 26) Any other reason, which in the opinion of the investigator, would make the subject not suitable for participation in the trial.

